3.1.2 Safety Evaluation Phase

3.1.2.1 Dose-Limiting Toxicity Assessment

The first 6 patients enrolled in the safety cohort will be eligible for DLT assessment. The DLT assessment window for the safety cohort is 56 days from the first dose of Hu5F9-G4.

All patients who experience a DLT during the DLT assessment window will be considered evaluable for safety evaluation decisions.

Patients who withdraw from study treatment (atezolizumab plus Hu5F9-G4) for any reason other than a DLT during this assessment window will not be considered evaluable for safety evaluation decisions and will be replaced. The total number of enrolled patients in this study will be capped at 21 patients. If patients are replaced prior to DLT assessment, discontinued patients will be counted toward the total limit of 21 patients.

During the DLT evaluation window, patients will not be allowed to make up missed doses; patients will resume dosing at their next scheduled dose. Patients who are unable to receive the next scheduled dose of Hu5F9-G4 or atezolizumab as a result of study treatment-related adverse events will be considered to have met the DLT criteria.

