3.1.2.2 Rules for Dose Modification and Changes in Dose Scheduling following Dose-Limiting Toxicity

Dose modification following the DLT window will occur in accordance with the following rules:

- The safety cohort will enroll up to 6 patients.
- *If DLTs are observed in ≥33% of patients (i.e., 2 or more of 6 patients) in this initial safety cohort, a dose de-escalation cohort of 6 patients will be enrolled. The dosing schedules for this de-escalation cohort will be as follows:*
 - *Atezolizumab will be administered to patients by IV infusion at a fixed dose of 840 mg, starting on Day 22 of Cycle 1. In subsequent cycles, 840 mg of atezolizumab administered by IV infusion will be given Q2W on Days 8 and 22 of each 28-day cycle.*
 - *Hu5F9-G4 will be given as two priming doses of 1 mg/kg IV on Days 1 and 4, followed by loading doses of 10 mg/kg IV on Day 8 and 15 mg/kg on Day 11. Starting on Day 15, maintenance treatment with Hu5F9-G4 will be given by IV infusion at a dose of 15 mg/kg QW.*
 - *If a DLT is observed in ≥33% of patients (i.e., 2 or more of 6 dose de-escalation patients), the dose and schedule will be considered intolerable and the MTD will have been exceeded.*

- The dose level(s) and schedule at which *<33% of patients (i.e., 1 or fewer of 6 dose de-escalation patients) experience a DLT will be declared the optimal dose and schedule and an expansion cohort of 9 patients will be enrolled using the same dosing regimen.*
- *If DLTs are observed in <33% of patients (i.e., 1 or fewer of 6 patients) in the initial safety cohort, an expansion cohort of 15 patients will be enrolled to further test the safety and anti-tumor activity of atezolizumab in combination with Hu5F9-G4, using the same dosing regimen.*

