- Grade 3 tumor lysis syndrome or electrolyte disturbances (hyperkalemia, hypophosphatemia, hyperuricemia, etc.) that resolve to Grade ≤ 2 or baseline value within 7 days
- Grade 3 or 4 lymphopenia or leukopenia
- Any Grade 3 autoimmune toxicity that clinically resolves to Grade ≤ 2 within 7 days of initiating therapy
- Grade 3 diarrhea or skin toxicity that resolves to Grade 1 or better in <7 days after medical management (e.g., immunosuppressant treatment) has been initiated
- Other single laboratory values out of normal range that have no clinical correlate and resolve to Grade ≤ 2 or to baseline within 7 days with adequate medical management
- Tumor flare phenomenon defined as local pain, irritation, or rash localized at sites

Appendix 8

Overall Guidelines for Management of Patients Who Experience Adverse Events (cont.)

Patients who are deemed to require further dose reductions <20 mg/kg of Hu5F9-G4 should be discontinued from study treatment with Hu5F9-G4.

TREATMENT INTERRUPTION

Atezolizumab treatment may be temporarily suspended in patients experiencing toxicity considered to be related to study treatment. If corticosteroids are initiated for treatment of the toxicity, they must be tapered over ≥ 1 month to the equivalent of ≤ 10 mg/day oral prednisone before atezolizumab can be resumed. If atezolizumab is withheld for > 12 weeks after event onset, the patient will be discontinued from atezolizumab. However, atezolizumab may be withheld for > 12 weeks to allow for patients to taper off corticosteroids prior to resuming treatment. Atezolizumab can be resumed after being withheld for > 12 weeks if the Medical Monitor agrees that the patient is likely to derive clinical benefit. Atezolizumab treatment may be suspended for reasons other than toxicity (e.g., surgical procedures) with Medical Monitor approval. The investigator and the Medical Monitor will determine the acceptable length of treatment interruption.

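### DLT evaluability sets no minimum exposure, so a safety-cohort patient who misses atezolizumab doses for unrelated reasons without withdrawing counts toward clearing the combination

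*Combined protocol and SAP*

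**What the plan says.** Section 3.1.2.1, repeated in the synopsis, sets the window: "The DLT assessment window for the safety cohort is 56 days from the first dose of Hu5F9-G4". Two sentences then decide who counts. "All patients who experience a DLT during the DLT assessment window will be considered evaluable for safety evaluation decisions". Against that, "Patients who withdraw from study treatment (atezolizumab plus Hu5F9-G4) for any reason other than a DLT during this assessment window will not be considered evaluable", and such patients are replaced within the cap of 21. No other ground for non-evaluability is given.

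On missed doses the section says that "patients will not be allowed to make up missed doses; patients will resume dosing at their next scheduled dose". One kind of missed dose is treated as toxicity: "Patients who are unable to receive the next scheduled dose of Hu5F9-G4 or atezolizumab as a result of study treatment-related adverse events" are taken to have met the DLT criteria.

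Other sections bear on the same count:

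- Section 3.1 applies the percentage rule to enrolled and dosed patients, without naming a drug or a number of doses. Section 6 defines only a safety-evaluable population (any amount of either drug) and no DLT-evaluable set.
- Section 3.1.2.2 clears the initial cohort at 0 or 1 DLT in 6. At the same count the de-escalated regimen "will be declared the optimal dose and schedule and an expansion cohort of 9 patients will be enrolled".
- Appendix 8 (Treatment Interruption) allows a pause without withdrawal: "Atezolizumab treatment may be suspended for reasons other than toxicity (e.g., surgical procedures) with Medical Monitor approval". It also says that stopping atezolizumab should end Hu5F9-G4 as well, whereas atezolizumab may continue after Hu5F9-G4 is stopped.

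**The concern.** The six-patient decision is meant to judge the combination. Atezolizumab starts three weeks into the window, so a few missed doses remove most or all of the combination exposure while the patient is still followed to Day 56. As the text stands, that patient has not withdrawn, has no DLT under the missed-dose rule, cannot make the doses up, and fills one of the six places.

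If under-exposure lowers the chance of a DLT, each such patient makes it easier to see 0 or 1 DLT. The error then runs toward declaring the regimen tolerated and opening expansion. Section 5.1.3 says that synergistic effects of the two drugs on the adverse event profile are unknown. Follow-up on Hu5F9-G4 alone therefore cannot stand in for follow-up on both.

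**Working it through.** **Planned doses in the window (Section 3.1.1).**

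- Hu5F9-G4: Days 1, 4, 8, 11, 15 and 22 of Cycle 1, then weekly in Cycle 2 (study Days 29, 36, 43, 50), giving 6 + 4 = 10.
- Atezolizumab: Day 22 of Cycle 1, then Days 8 and 22 of Cycle 2, which are study Days 28 + 8 = 36 and 28 + 22 = 50. That gives 3.

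**Days on which the combination can be observed.** From Day 22 to Day 56 inclusive there are 56 − 22 + 1 = 35. If the first atezolizumab dose is missed, 56 − 36 + 1 = 21. If the first two are missed, 56 − 50 + 1 = 7. If all three are missed, none.

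**The plan's threshold.** 2/6 = 33.3% and 1/6 = 16.7%, so 2 or more of 6 meets the 33% limit and 1 or fewer does not. This reproduces.

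**Effect of one under-exposed patient.** The documents state no true DLT rate, so the values below are assumptions. Let p be the true rate in a fully exposed patient and q the rate in one under-exposed patient, with patients independent. With five patients at rate p, write

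- A = P(at most 1 DLT in 5) = (1−p)^5 + 5p(1−p)^4
- B = P(no DLT in 5) = (1−p)^5

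Then P(cohort cleared) = (1−q)A + qB. Setting q = p gives the intended six-patient rule. Since A exceeds B, any q below p raises the chance of clearing.

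At p = 0.33, A = 0.4675 and B = 0.1350:

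- q = 0.33: 0.67 × 0.4675 + 0.33 × 0.1350 = 0.358
- q = 0.165: 0.835 × 0.4675 + 0.165 × 0.1350 = 0.413
- q = 0: 0.468

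At p = 0.40, A = 0.3370 and B = 0.0778:

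- q = 0.40: 0.60 × 0.3370 + 0.40 × 0.0778 = 0.233
- q = 0.20: 0.80 × 0.3370 + 0.20 × 0.0778 = 0.285
- q = 0: 0.337

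| True DLT rate p (assumed) | All six fully exposed | One patient, risk halved | One patient, zero risk |
|---|---|---|---|
| 0.20 | 65.5% | 69.6% | 73.7% |
| 0.33 | 35.8% | 41.3% | 46.8% |
| 0.40 | 23.3% | 28.5% | 33.7% |
| 0.50 | 10.9% | 14.8% | 18.8% |

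**Which missed doses the text already handles.**

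| Situation in the window | Outcome as written |
|---|---|
| Next dose of either drug missed because of a related adverse event | Counts as a DLT (3.1.2.1) |
| Atezolizumab permanently stopped, no DLT | Hu5F9-G4 should stop too (Appendix 8), so a withdrawal, and replaced |
| Atezolizumab doses missed for an unrelated reason, no withdrawal | Evaluable and DLT-free |
| Hu5F9-G4 stopped for an unrelated reason, atezolizumab continued | Evaluable and DLT-free, if withdrawal means leaving both drugs |

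The last two rows are the gap.

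**The case against.** The case against is substantial. Adverse events that stop dosing lean toward being DLTs, because Table 6 in Section 5.3.4 makes relatedness the default. Suspension of atezolizumab for other reasons needs Medical Monitor approval, and planned major surgery is an exclusion criterion. Three or more consecutive missed Hu5F9-G4 doses prompt a decision on permanent discontinuation. Clearance is not purely mechanical: Section 4.2 wants the six patients fully assessed and judged to be tolerating study treatment, Section 3.1.2.3 has the sponsor review the relevant data, and Table 1 gives the expansion cohort its own stopping boundaries.

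This narrows the gap without closing it. None of these provisions says how much of each drug a DLT-free patient must have received, and the stopping boundaries act only after expansion has opened.

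A reader might infer more than the documents support, in four ways.

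- *Any patient on one drug alone counts.* Stopping atezolizumab should end Hu5F9-G4, so only the reverse case remains. Even that depends on reading withdrawal as leaving both drugs; because Section 2 defines study treatment as the combination, leaving either drug could also be meant.
- *The WBC limit explains missed atezolizumab.* Section 4.1.1 applies it before the first dose and before Hu5F9-G4 doses in Cycle 1. It does not expressly govern atezolizumab.
- *An under-exposed patient cannot have a DLT.* Section 3.1.2.3 counts events related to Hu5F9-G4 alone, so zero risk is a bound and not an estimate.
- *The cohort will probably be cleared in error.* The documents give no frequency of such patients.

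**Conclusion.** The concern holds, limited to doses missed for reasons unrelated to study treatment in patients who have not withdrawn, and to the one-drug case if withdrawal means both drugs. Within those limits it is a stated counting rule that favours clearing the regimen, on a schedule with only three atezolizumab doses in the window.

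One such patient among six adds about 5 to 11 percentage points to the chance of clearing at an assumed true DLT rate of 33%, and about 5 to 10 points at 40%. The lower end halves that patient's DLT risk and the upper end removes it. These figures rest on assumed rates, independent patients and exactly one under-exposed patient. If under-exposure did not lower the risk, there would be no shift. The absence of an exposure requirement rests on the text alone and needs none of these assumptions.

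**What to change.** In Section 3.1.2.1 and the synopsis, define a DLT-evaluable patient as one who (a) has a DLT at any time in the 56-day window, or (b) completes the window having received a prespecified minimum number of the planned doses of each drug. The sponsor sets the minimum. State whether leaving one drug counts as withdrawal. Replace patients who meet neither condition, within the cap of 21, and apply the 2-of-6 rule to evaluable patients only. In the DLT listing, show doses of each drug received beside DLT status.

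Two passages must be reconciled with this. Section 3.1.2.2 limits the safety cohort to at most 6 enrolled patients, which leaves no room for replacements. Section 4.6.1 says that patients who discontinue treatment early are not replaced, whereas Section 3.1.2.1 says that those who leave in the window are.

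The cost is a few sentences and an occasional extra replacement. Both planned paths use the whole cap (6 + 15 = 21, and 6 + 6 + 9 = 21), so each replacement takes a place from the expansion cohort. No patient leaves the safety-evaluable population, and no dose or treatment rule changes.

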3.1.1 Overview of Study Design

[Figure 1](#) presents an overview of the study design. A schedule of activities is provided in [Appendix 1](#).

Figure 1 Study Schema

Atezo=atezolizumab; DLT=dose-limiting toxicity; Q2W=every 2 weeks; QW=once a week.

Note: On days when both atezolizumab and Hu5F9-G4 are administered (Day 22 of Cycle 1 and Days 8 and 22 of subsequent cycles), Hu5F9-G4 should be administered first and *the interval between Hu5F9-G4 and atezolizumab infusions should follow guidelines as outlined in [Table 2](#).*

The proposed treatment regimen during Cycle 1 is a biomarker-driven treatment plan designed to assess the effect of single-agent Hu5F9-G4 on markers of immune activation in AML. This safety cohort is designed to assess the safety, tolerability, and clinical activity of Hu5F9-G4 in combination with atezolizumab based on the following schedule:

- Atezolizumab: Atezolizumab will be administered to patients by IV infusion at a fixed dose of 840 mg, starting on Day 22 of Cycle 1. In subsequent cycles (Cycles 2 and beyond), 840 mg of IV atezolizumab will be given every 2 weeks (Q2W) on Days 8 and 22 of each 28-day cycle.
- Hu5F9-G4: Two priming doses of 1 mg/kg of Hu5F9-G4 will be administered to patients by continuous IV infusion on Days 1 and 4 of Cycle 1, followed by loading doses of 15 mg/kg IV on Day 8 and 30 mg/kg IV on Day 11. Starting on Day 15 of Cycle 1, Hu5F9-G4 maintenance will be given by IV infusion at a dose of 30 mg/kg once a week (QW) of each 28-day cycle. On days when both atezolizumab and Hu5F9-G4 are administered (Day 22 of Cycle 1 and Days 8 and 22 of subsequent cycles), Hu5F9-G4 should be administered first and *the interval between Hu5F9-G4 and atezolizumab infusions should follow guidelines as outlined in Table 2*.

If DLTs are observed in $\geq 33\%$ of patients (i.e., 2 or more of 6 patients) in this initial safety cohort, a dose de-escalation cohort of 6 patients will be enrolled. The dosing schedules for this de-escalation cohort will be as follows:

- Atezolizumab will be administered to patients by IV infusion at a fixed dose of 840 mg, starting on Day 22 of Cycle 1. In subsequent cycles, 840 mg of atezolizumab administered by IV infusion will be given Q2W on Days 8 and 22 of each 28-day cycle.

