- Hu5F9-G4 will be given as two priming doses of 1 mg/kg IV on Days 1 and 4, followed by loading doses of 10 mg/kg IV on Day 8 and 15 mg/kg on Day 11. Starting on Day 15, maintenance treatment with Hu5F9-G4 will be given by IV infusion at a dose of 15 mg/kg QW.
- If $<33\%$ (i.e., 1 or fewer of 6 patients) *patients in the de-escalation cohort experience a DLT*, an expansion cohort of 9 patients will be enrolled to further test the safety and anti-tumor activity of atezolizumab in combination with Hu5F9-G4, using the same dosing regimen

If DLTs are observed in $<33\%$ of patients (i.e., 1 or fewer of 6 patients) in the initial safety cohort, an expansion cohort of 15 patients will be enrolled to further test the safety and anti-tumor activity of atezolizumab in combination with Hu5F9-G4, using the same dosing regimen.

Study treatment will be administered until unacceptable toxicity or loss of clinical benefit, as determined by the investigator, after local biopsy results (if available) and clinical status (e.g., symptomatic deterioration such as pain secondary to disease) are assessed.

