Between 10% and 40% of newly diagnosed patients with AML do not achieve CR with intensive induction therapy and are therefore categorized as having disease that is primary refractory or resistant. In addition, between 30% and 80% of patients who achieve a CR will subsequently relapse. Few of these patients can be cured with conventional salvage therapy (Thol et al. 2015). Most patients with R/R AML should be enrolled in clinical trials, given that highly effective and standardized treatments for AML are lacking and clinical trial enrollment is encouraged in this population.

3.3.4 **Rationale for Hu5F9-G4 Dose**

The dosing schedule chosen for Hu5F9-G4 was established during the Phase I clinical trial, during which no MTD was identified at doses of up to 30 mg/kg twice a week. In addition, PD assessments, conducted during the same Phase I clinical trial demonstrated that a priming dose for the first week, followed by escalating doses during the second week, and subsequently by weekly doses of the anti-CD47 monoclonal antibody, was not associated with early deaths, was safe and well tolerated in AML patients, resulted in a linear PK profile (see [Figure 2](#)), and optimal CD47 antigen binding in bone marrow at steady state (see [Figure 2](#)).

Figure 2 Hu5F9-G4 Achieves Target PK Levels at Clinically Feasible Doses

- 5F9 can overcome the CD47 antigen sink at 10 mg/kg or higher
- Antibody half-life is ~13 days
- Free plasma drug levels exceed preclinical activity thresholds identified from PK modeling (>100 to 250 μg/ml)

5F9 = Hu5F9-G4; PK = pharmacokinetic.

Source: Agoram et al. 2018.

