4.3.2.2 Hu5F9-G4

The initial priming dose will be administered as a continuous IV infusion in 250 mL of normal saline over 180 minutes to reduce the risk of acute hemagglutination. All other infusions for doses > 1 mg/kg will be administered in 500 mL over 120 minutes. If more than 4 weeks have elapsed since the last dose of Hu5F9-G4 and the patient is to resume treatment, patients must undergo intra-patient dose escalation again of Hu5F9-G4 based on their original dosing regimen (e.g., 1 mg/kg of priming dose on Days 1 and 4, 15 mg/kg on Day 8, and 30 mg/kg on Days 11, 15, and 22).

The dose level of Hu5F9-G4 administered to patients by IV infusion in this study varies according to the week of treatment. Initially, two priming doses of 1 mg/kg will be given on Days 1 and 4 of Cycle 1. This will be followed by loading doses of 15 mg/kg on Day 8, followed by 30 mg/kg on Day 11 of Cycle 1. Starting on Day 15, Hu5F9-G4 maintenance will be given at a dose of 30 mg/kg QW.

Premedication is required before administration of the first four doses of Hu5F9-G4 with 650–1000 mg of oral acetaminophen and 25–50 mg of oral or IV diphenhydramine or comparable regimen.

Recommended safety measures for preparation and handling of Hu5F9-G4 include laboratory coats and gloves. In addition, Hu5F9-G4 cannot be mixed with any other drug in the infusion bag or administration. Hu5F9-G4 should not be administered as a bolus injection.

There have been no late-onset hypersensitivity reactions. Thus, recommendations for potential infusion reactions should follow recommendations from [Table 2](#) (see Section 4.3.2.1). Guidelines for medical management of infusion-related reactions (IRRs) are provided in the [Appendix 8](#).

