Cycle 1, Day 8	Prior to the first infusion of Hu5F9-G4	
 • Hu5F9-G4 PK (serum)
	1 hour (\pm 15 minutes) after the end of the infusion of Hu5F9-G4	
 • Hu5F9-G4 PK (serum)
Cycle 1, Day 11	Prior to the first infusion	
 • Hu5F9-G4 PK (serum)
	1 hour (\pm 15 minutes) after the end of the infusion of Hu5F9-G4	
 • Hu5F9-G4 PK (serum)
Cycle 1, Day 22	Prior to the first infusion of Hu5F9-G4 and atezolizumab	
 • Atezolizumab PK (serum) • Hu5F9-G4 PK (serum) • Atezolizumab ADA (serum)
	30 (\pm 10) minutes after the atezolizumab infusion	
 • Atezolizumab PK (serum)
	1 hour (\pm 15 minutes) after the end of the infusion of Hu5F9-G4	
 • Hu5F9-G4 PK (serum)
Cycle 2, Day 1	Prior to the first infusion of Hu5F9-G4	
 • Hu5F9-G4 PK (serum) • Hu5F9-G4 ADA (serum)
	1 hour (\pm 15 minutes) after the end of the infusion of Hu5F9-G4	
 • Hu5F9-G4 PK (serum)

ADA=anti-drug antibody; PK=pharmacokinetic.

Note: Except for Day 1 of Cycle 1, all other study visits and assessments during the treatment period should be performed within \pm 3 days of the scheduled date. Study assessments may be delayed or moved ahead of the window to accommodate holidays, vacations, and unforeseen delays.

Appendix 2
Schedule of Pharmacokinetic and Immunogenicity Samples
(cont.)

Visit	Timepoint(s)	Sample Type
Cycle 2, Day 8	Prior to the first infusion	
 • Atezolizumab PK (serum) • Hu5F9-G4 PK (serum) • Atezolizumab ADA (serum)
Cycle 2, Day 22	Prior to the first infusion	
 • Atezolizumab (PK serum) • Atezolizumab ADA (serum)
Cycle 3, Day 1	Prior to the first infusion	
 • Hu5F9-G4 PK (serum) • Hu5F9-G4 ADA (serum)
	1 hour (\pm 15 minutes) after the end of the infusion of Hu5F9-G4	
 • Hu5F9-G4 PK (serum)
Cycle 3, Day 22	Prior to the first infusion	
 • Atezolizumab PK (serum) • Atezolizumab ADA (serum)
Cycle 4, Day 22	Prior to the first infusion	
 • Atezolizumab PK (serum) • Atezolizumab ADA (serum)
Cycle 5, Day 1	Prior to the first infusion	
 • Hu5F9-G4 PK (serum) • Hu5F9-G4 ADA (serum)

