Hu5F9-G4 treatment may be temporarily suspended in patients experiencing toxicity considered to be related to study treatment (see the Dose Modifications section). If a patient misses three or more consecutive doses during the combination treatment period, the investigator and Medical Monitor will decide whether the patient should discontinue Hu5F9-G4 permanently. If Hu5F9-G4 is withheld for > 28 days because of toxicity, the patient should be discontinued from Hu5F9-G4. However, if the investigator believes the patient is likely to derive clinical benefit and the Medical Monitor is in agreement, Hu5F9-G4 can be resumed after being withheld for > 28 days. If the time interval between Hu5F9-G4 doses is > 4 weeks on account of missed doses, a repriming period is required prior to restarting weekly doses. If repriming is necessary, atezolizumab should be held during the repriming week and restarted when the 30-mg/kg weekly dosing of Hu5F9-G4 begins.

If atezolizumab is discontinued, Hu5F9-G4 should also be discontinued. If Hu5F9-G4 is discontinued, atezolizumab can be continued if the patient is likely to derive clinical benefit, as determined by the investigator.

MANAGEMENT GUIDELINES

Guidelines for the management of patients who experience specific adverse events are provided in [Appendix 9](#) for atezolizumab-related adverse events and in the Atezolizumab Investigator's Brochure. This section integrates management guidelines for those adverse events when both atezolizumab and Hu5F9-G4 have developed guidance. This section also includes generic guidance for management of Hu5F9-G4.

Appendix 8

Overall Guidelines for Management of Patients Who Experience Adverse Events (cont.)

when atezolizumab-associated adverse events occur. This section includes management guidelines for Hu5F9-G4-associated adverse events. For cases in which management guidelines are not covered in [Appendix 9](#), the Hu5F9-G4 Investigator's Brochure, or the protocol, patients should be managed as deemed appropriate by the investigator according to best medical judgment.

INFUSION-RELATED REACTIONS AND ANAPHYLAXIS

Management guidelines for patients who experience infusion-related reactions or anaphylaxis are presented in [Table 1](#).

Table 1 Guidelines for Management of Patients Who Experience Adverse Events Associated with Hu5F9-G4

Event	Action to Be Taken
IRRs and anaphylaxis	

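### In the full-dose safety cohort, the no-make-up rule takes a patient who misses the Day 8 dose for a non-treatment-related reason from 1 to 30 mg/kg of Hu5F9-G4

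*Combined protocol and SAP*

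**What the plan says.** Section 3.1.1 sets the Hu5F9-G4 step-up for the full-dose safety cohort: 1 mg/kg on Days 1 and 4, "followed by loading doses of 15 mg/kg IV on Day 8 and 30 mg/kg IV on Day 11", then 30 mg/kg weekly from Day 15. The de-escalation cohort has the same priming, "loading doses of 10 mg/kg IV on Day 8 and 15 mg/kg on Day 11", then 15 mg/kg weekly.

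Section 3.1.2.1 governs missed doses in the 56-day window for dose-limiting toxicity (DLT): "During the DLT evaluation window, patients will not be allowed to make up missed doses; patients will resume dosing at their next scheduled dose". A dose missed because of a treatment-related adverse event is itself a DLT. A dose missed for another reason is not.

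Two places bring back the low starting dose, both only after a gap of more than 4 weeks. Section 4.3.2.2 says "patients must undergo intra-patient dose escalation again of Hu5F9-G4 based on their original dosing regimen". Appendix 8 (Treatment Interruption) says that after such a gap "on account of missed doses, a repriming period is required prior to restarting weekly doses".

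Section 3.3.4 rests its tolerability statement on a Phase I sequence of "a priming dose for the first week, followed by escalating doses during the second week", with weekly doses after that.

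**The concern.** The protocol itself provides a non-toxic reason to hold a dose. Section 4.1.1 requires WBC at or below 20 x 10^3/µL before each Cycle 1 dose of Hu5F9-G4 and allows hydroxyurea to reach it. A patient whose count is too high on Day 8 may miss the 15 mg/kg dose with no DLT recorded. Followed to the letter, the protocol then gives that patient 30 mg/kg as the first dose after 1 mg/kg.

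The patient has left the escalating second-week sequence that Section 3.3.4 relies on but stays in the dose decision. Section 3.1.2.1 says "All patients who experience a DLT during the DLT assessment window will be considered evaluable for safety evaluation decisions", and only withdrawal from study treatment for a reason other than a DLT makes a patient non-evaluable. Nothing says how a DLT after an altered step-up should be read when the 2-of-6 rule is applied.

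**Working it through.** The plan states no figure on this point, so the check follows the dosing rules day by day for a patient whose last dose was 1 mg/kg on Day 4.

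1. **Next scheduled dose, full-dose cohort (Sections 3.1.1 and 3.1.2.1).** With Day 8 missed and not made up, the remaining doses fall on Days 11, 15, 22 and 29, and each is 30 mg/kg. The first step after priming is 30/1 = 30-fold. As planned it is 15/1 = 15-fold, followed by 30/15 = 2-fold.

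2. **Repriming (Section 4.3.2.2, Appendix 8).** More than 4 weeks means more than 28 days. Since 4 + 28 = 32, repriming starts to apply on Day 33. Up to Day 32 it does not.

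3. **Other rules that might restore the 15 mg/kg step.**
   - The rescheduling rule in Section 4.5 covers holidays and weekends.
   - The WBC limit (Section 4.1.1) and the pre-dose clinical and laboratory check (Section 4.5) decide whether to dose, not which dose to give.
   - The rule in Appendix 8 on three or more consecutive missed doses concerns the combination period and the decision to discontinue.

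   None of these requires 15 mg/kg before 30 mg/kg.

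4. **Day 11 and the visit window.** A note in Appendix 2 says that, apart from Cycle 1 Day 1, "all other study visits and assessments during the treatment period should be performed within" 3 days either side of the scheduled date.
   - If the note governs dosing, the Day 8 visit runs to 8 + 3 = Day 11. Day 11 then falls in the windows of both the 15 mg/kg and the 30 mg/kg dose, and the text does not say which is given.
   - If the note governs only the sampling schedule in which it sits, there is no ambiguity: a patient not dosed on Day 8 receives 30 mg/kg on Day 11, and the step is already skipped.
   - The note goes on to let assessments move for unforeseen delays. If it governs dosing, the end of the Day 8 window is therefore not firm.

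5. **De-escalation cohort.** The planned sequence is 1, 1, 10, 15 mg/kg. With Day 8 missed the step is 1 to 15 mg/kg, 15/1 = 15-fold instead of 10/1 = 10-fold. That equals the Day 8 step planned for the full-dose cohort.

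**The case against.** Read by nominal dates, Section 3.1.2.1 is a clear rule, and barring make-up doses in a DLT window is a defensible choice. The hazard is not shown. Section 5.1.2 credits priming and maintenance dosing with mitigating the acute hematologic effects, and this patient has had both priming doses. Section 3.3.4 reports no maximum tolerated dose at up to 30 mg/kg twice a week, and it supports the sequence as a whole without singling out the 15 mg/kg step as protective. Premedication covers the first four doses, so it would cover this one. The reach is narrow: one small cohort, and only holds unrelated to treatment, where Table 6 presumes that an adverse event is related. Hydroxyurea should prevent some WBC holds. The Sponsor reviews relevant data before dose-modification decisions, Section 6.3 flags dose modifications in the listing, and an extra counted DLT pushes toward the lower dose.

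Most of this stands, and it limits the point to a minor one. It does not close the gap. None of these provisions tells a site to give 15 mg/kg before 30 mg/kg, and review afterwards does not change what the patient received. The repriming example in Section 4.3.2.2 puts 15 mg/kg before 30 mg/kg again, so the sponsor treats that step as part of the ladder.

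A reader might go further and infer that the skipped step biases the 2-of-6 decision by a calculable amount. The documents do not support that. Comparing the chance of de-escalation once a DLT has occurred with the unconditional chance would show only the effect of already having one DLT; the same gap would follow a DLT in a patient dosed exactly on schedule.

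**Conclusion.** The gap is real and minor. In the DLT window of the full-dose safety cohort, a hold that is not treatment-related, begins after the Day 4 dose and causes the Day 8 dose to be missed leads to a first post-priming dose of 30 mg/kg, unless the gap from Day 4 exceeds 4 weeks. In the de-escalation cohort the corresponding dose is 15 mg/kg, a lesser concern.

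The size is a 30-fold step in place of a 15-fold one. It would be tempting to read that as a measure of risk, or to state a fixed number of days on which a patient is unprotected. Neither is supported: the documents give no excess hazard and no rate of such holds, and the Appendix 2 note leaves the end of the Day 8 window uncertain. The conclusion on the skipped step does not depend on how that note is read; only the Day 11 ambiguity does.

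**What to change.** - **Section 3.1.2.1:** exempt the Cycle 1 step-up doses of Hu5F9-G4 from the rule that dosing resumes at the next scheduled dose.
- **Section 4.3.2.2:** require the intermediate loading dose (15 mg/kg, or 10 mg/kg if de-escalated) before any higher dose, at least 3 days before the next step, and say that this holds on Day 11 too. If the intermediate dose falls on Day 15 or later, the Sponsor and Medical Monitor decide whether the Day 22 sample and first atezolizumab dose move.
- **DLT review:** flag any DLT that follows an altered step-up.

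The cost is two short edits, one flag, and lower Hu5F9-G4 exposure before the Day 22 sample in patients already off schedule. That matters because Section 4.3.2.1 times the sample to Hu5F9-G4 steady state. Cumulative dose before Day 22 in the full-dose cohort, planned as 1 + 1 + 15 + 30 + 30 = 77 mg/kg, becomes:

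- **Dosing resumes on Day 11, next dose Day 15:** 1 + 1 + 15 + 30 = 47 mg/kg with the fix, against 1 + 1 + 30 + 30 = 62 when 30 mg/kg is given on Day 11.
- **Dosing resumes on Day 15, Day 22 kept:** 1 + 1 + 15 = 17 mg/kg with the fix, against 1 + 1 + 30 = 32 under the current rule.
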